#### 6.1.3 PRODUCT STORAGE AND STABILITY

Both Climara and Prometrium can be stored at room temperature for the duration of an individual's study participation. Participants will be instructed to avoid exposing study drugs to extreme temperatures or humidity. More specific information about storage and stability can also be found in the attached inserts for Climara and Prometrium.

#### 6.1.4 PREPARATION

All preparation will be handled by UNC Investigational Drug Services (IDS), who will blind and mask the study drugs. No further preparation will be required by study staff or participants.

#### 6.1.5 DOSING AND ADMINISTRATION

Dosages of E2 and P4 will be fixed. Dosages will not be tied to meals, but will be 12 hours apart in the morning and evening.

#### 6.1.6 ROUTE OF ADMINISTRATION

E2 will be administered via transdermal patch. Micronized P4 will be administered orally in pill form.

#### 6.1.7 STARTING DOSE AND DOSE ESCALATION SCHEDULE

In the experimental arm, the dosages will be fixed and not changed.

#### 6.1.8 DOSE ADJUSTMENTS/MODIFICATIONS/DELAYS

If the PI and her supervisors determine that a participant must be discontinued from the protocol (see Section 5.4.2), [name] will be unblinded via IDS. If the participant was on active E2/P4, [name] will supervise the subject's discontinuation from E2/P4. Regardless of the condition the participant was in, the PI will continue to follow the participant until appropriate clinical care is administered (e.g., hospitalization for suicidality).

#### 6.1.9 DURATION OF THERAPY

The planned duration of active treatment is 14 days. All days in which participants use patches and pills will be utilized in multilevel modeling analyses, which accommodate unbalanced/missing data.

#### 6.1.10 TRACKING OF DOSE

**For patches (E2):** E2 patches will be applied (day +7 following ovulation) and changed (day +14 following ovulation) in the laboratory; therefore, no compliance issues are anticipated for E2. One extra patch will be given to each participant in the case that the patch falls off. All used patches will be brought to the lab so that use of patches can be monitored.

**For pills (P4):** at the first lab visit, study staff will work with participants to develop individualized methods for reminding the participant to take twice-daily study pills, including but not limited to email reminders, phone call reminders, text reminders, app-based reminders (with data stored locally only), pill charts, calendar reminders, and stimulus control (e.g., putting study medication on bedside table. Women will bring in pill bottles to each visit so compliance can be monitored.

#### 6.1.11 DEVICE SPECIFIC CONSIDERATIONS

Not applicable.

### 6.2 STUDY AGENT ACCOUNTABILITY PROCEDURES

Research staff pick up agents from IDS and distribute to subjects as outlined in the study schedule below. All unused pills and patches will be returned to study staff, who will return them to IDS. IDS will dispose of unused materials according to regulations.

## 7 STUDY PROCEDURES AND SCHEDULE

### 7.1 STUDY PROCEDURES/EVALUATIONS

#### 7.1.1 STUDY SPECIFIC PROCEDURES

##### PHONE SCREENING

Variable	Interview Measure	Self-Report Measure	Task Measure
Inclusion/Exclusion Criteria	X	-	-
Psychiatric Diagnosis	Self-reported Previous Diagnosis	-	-
Suicidality	Abbreviated SITBI	-	-

### ENROLLMENT VISIT – 1 [contact] HRS

- **Timing:** Can occur at any time provided that it allows for the participant to complete the protocol in the term of IRB approval.
- **Assessments Administered (see section 4.1 for Abbreviations):**

Variable	Interview Measure	Self-Report Measure	Task Measure
Vitals	-	-	Height/Weight
Urine Pregnancy Screen	-	-	X
Inclusion/Exclusion Criteria	X		
Psychiatric Diagnosis	SCID	-	-
Suicidality	Full SITBI	-	-
Depression	-	CESD	-
Hopelessness	-	BHI	-
Inhibitory Control	-	UPPS-P	-
Threat Sensitivity	-	STAI	-
Negative Social Appraisals	-	SSES	-

### LABORATORY TESTING VISITS – 6 [contact] HRS

- **Timing:** The three laboratory visits for each condition will occur on days +7, +14, and +22 following positive ovulation test (day 0). The acceptable windows will be +/- 2 days in either direction for each visit.
- **Assessments Administered (see section 4.1 for Abbreviations):**

Variable	Interview Measure	Self-Report Measure	Task Measure
Urine Pregnancy Screen (3 rd visit only)	-	-	X
Blood Sample (10 ml tube)	-	-	Serum E2/P4
Suicidality	Full SITBI	-	-
Depression	-	CESD	-
Hopelessness	-	BHI	FT-IRAP
Inhibitory Control	-	UPPS-P	SST
Threat Sensitivity	-	STAI	DPT

Negative Social Appraisals	-	SSES	SAR-IAT
Side Effects and Compliance Monitoring	X	-	-

## DEBRIEFING VISIT – 30 MINUTES

- **Timing:** Debriefing will occur within a 15 day window following completion of the second condition.
- Individual results will not be reported to the patient.
- Referral to original care provider will be facilitated as necessary.
- **Assessments Administered (see section 4.1 for Abbreviations):**

Variable	Interview Measure	Self-Report Measure	Task Measure
Final Suicide Risk Assessment	Full SITBI	-	-

### 7.1.2 STANDARD OF CARE STUDY PROCEDURES

Although the LRAP/UWRAP dictates the provision of basic supportive conversation and other simple interventions to reduce imminent risk in the context of increased suicidality, participants are expected to utilize their mental health provider for any **treatment** needs that arise during the course of the study. Therefore, participation will require that the participant consents to phone contact between the PI and their current mental health provider in two circumstances: (1) one standard phone contact occurring prior to engagement in the first condition in which the PI describes the experiment and explains the protocol for daily risk assessment and discontinuation of participation should it be necessary; and (2) as-needed phone contact in the event that the participant must be discontinued to alert the provider to the severe change in mood symptoms or suicidality.

## 7.2 LABORATORY PROCEDURES/EVALUATIONS

### 7.2.1 CLINICAL LABORATORY EVALUATIONS

A point-of-care urine **pregnancy test** will be completed in our laboratory on site on two occasions: prior to randomization at the enrollment visit, and at the third study visit of the first condition.

At all 6 laboratory assessments during active treatment with placebo or E2/P4, women will provide 10ml **blood samples** to be assayed for E2/P4 to evaluate the success of the hormone in achieving stable luteal phase levels of E2/P4. [name]'s laboratory at UNC will conduct assays. Storage onsite will be handled by medical technician [name] in [name] laboratory.

### 7.2.3 SPECIMEN PREPARATION, HANDLING, AND STORAGE

Blood will be centrifuged and serum will be aliquotted into storage tubes and stored in a -80 F freezer in [name] lab. Standard freezer-proof labels will indicate participant

ID and study session. These will be transported under dry ice conditions to [name] laboratory in batches. Following assay, any additional serum will be stored in [name] laboratory.

#### 7.2.4 SPECIMEN SHIPMENT

Serum transport will be handled by [name] to [name]'s Bioendocrine lab under dry ice conditions. Samples will be sent in batches when there are enough aliquots to support purchase of RIA kits.

### 7.3 STUDY SCHEDULE

#### 7.3.1 SCREENING

The screening procedures described below must take place prior to the enrollment visit; because all information about eligibility obtained during the phone screen is confirmed at the enrollment visit, there is no expiration of screening procedures after which they must be repeated.

Women will be recruited primarily through chart review at the UNC outpatient psychiatry clinic; only those women agreeing to be recontacted for research procedures can be contacted. [name] will identify women via chart review who may be eligible for the study, and contact them to explain the study, and conduct phone screening in interested individuals.

Following verbal consent, verbal phone screening will include verbal assessment of all inclusion/exclusion criteria described above, including assessment of recent suicidality using the shortened SITBI.

#### 7.3.2 ENROLLMENT/BASELINE

Following recruitment screening via telephone, interested individuals will schedule and attend an enrollment visit at which they will provide informed consent and be further assessed for eligibility; assessment for eligibility includes assessment of height and weight (BMI), urine HcG pregnancy test, consent to contact their mental health provider at appropriate intervals for study participation, and other self-reported inclusion/exclusion criteria (including appropriate level of suicide risk on the SITBI-- see information in section 5.1). If ineligible, they will be referred back to their mental health provider and receive payment for the enrollment visit. If eligibility is confirmed, they will be further characterized using the SCID-I and SCID-II and complete various psychosocial questionnaires. In addition, they will be trained in the protocol for urine ovulation testing, daily telephone assessments, and the patch/pill administration schedule. Participants will be randomized to one of two possible condition orders at that time.

Pregnancy test must be negative in order for the participant to continue with the study. The study agent will not be administered until Lab assessment 1 (i.e., not at baseline/enrollment).

#### 7.3.3 FOLLOW-UP

Following the baseline/enrollment visit, women will remain in contact with study staff and will begin ovulation testing as instructed. When ovulation testing is positive (day 0), the participant will contact the study staff to schedule the first three laboratory assessment visits (visits for condition 1) on days +7, +14, and +22. All laboratory assessment visits are identical in structure and content, with the singular exception that the third laboratory visit in the first condition will include a pregnancy test that must be negative prior to starting the second condition. When the first condition is completed and the second pregnancy test is negative at the third laboratory visit, women will again remain in contact with study staff to schedule ovulation testing in the next menstrual cycle. Once again, when ovulation is confirmed (day 0), the final 3 laboratory assessments (for condition 2) will be scheduled on days +7, +14, and +22. These visits may be scheduled up to +/-2 days in either direction.

- **Follow-Up Assessments Administered (see section 4.1 for Abbreviations):**

Variable	Interview Measure	Self-Report Measure	Task Measure
Vitals	-	-	Weight
Urine Pregnancy Screen (3 rd follow-up only)	-	-	X
Blood Sample (10 ml tube)	-	-	Serum E2/P4
Suicidality	Full SITBI	-	-
Depression	-	CESD	-
Hopelessness	-	BHI	FT-IRAP
Inhibitory Control	-	UPPS-P	SST
Threat Sensitivity	-	STAI	DPT
Negative Social Appraisals	-	SSES	SAR-IAT
Side Effects, AEs, and Compliance Monitoring	X	-	-

**Follow-Up Timeline:**

**Condition 1 (Follow-Up Visits 1-3):**

- Negative Pregnancy Test Confirmed at Enrollment
- Ovulation Testing
- Positive Ovulation Test #1= Day 0
- Study Followup Visits 1-3 Scheduled for days +7, +14, +22
- Study Followup Visit 1 (Day +7): Assessments, administration of study agent patch A and dispensation of pills (**Condition 1**)
- Study Followup Visit 2 (Day +14): Assessments, replacement of study agent patch A with patch B (**Condition 1**)
- Removal of study patch and end of pills on day +21
- Study Followup Visit 3 (Day +22): Assessments, Pregnancy Test

**Condition 2 (Follow-Up Visits 4-6):**

- Negative Pregnancy Test Confirmed at Visit 3
- Ovulation Testing

- Positive Ovulation Test #2= Day 0
- Study Followup Visits 4-6 Scheduled for days +7, +14, +22
- Study Followup Visit 4 (Day +7): Assessments, administration of study agent patch A and dispensation of pills (**Condition 2**)
- Study Followup Visit 5 (Day +14): Assessments, replacement of study agent patch A with patch B (**Condition 2**)
- Removal of study patch and end of pills on day +21
- Study Followup Visit 6 (Day +22): Assessments, Schedule Debriefing

---

#### 7.3.4 FINAL STUDY VISIT

Debriefing visits will be scheduled within 15 days of study completion. In this final visit, a final risk assessment will be conducted and the participant will be referred as appropriate for additional clinical care. This final risk evaluation visit is included in order to reduce the likelihood of emergent risk following withdrawal from exogenous hormones in women who had the placebo-experimental condition order. Participants will not be provided with individualized study results.

---

#### 7.3.5 EARLY TERMINATION VISIT

Should early termination be deemed necessary (following procedures detailed above), and the situation does not involve a need for immediate hospitalization of the participant, then the participant will be invited to an early termination visit in which the full typical debriefing interview (i.e., risk assessment and referral as appropriate) will be conducted.

---

#### 7.3.6 UNSCHEDULED VISIT

There will be no unscheduled visits. Should a participant present at the laboratory at the wrong time, a member of the study staff will reschedule the visit if needed or refer her to her mental health provider as appropriate.

### 7.3.7 SCHEDULE OF EVENTS TABLE

Procedures	Screening	Enrollment/Baseline	IDS RANDOMIZATION	Follow-Up (Condition 1, Visit 1)	Follow-Up (Condition 1, Visit 2)	Follow-Up (Condition 1, Visit 3)	Follow-Up (Condition 2, Visit 4)	Follow-Up (Condition 2, Visit 5)	Follow-Up (Condition 2, Visit 6)	Final Visit/Debriefing Visit
Informed Consent	Verbal x	Written x								
Demographics	x	x								
Medical History/Inclusion/Exclusion Criteria	x	x								
SCID – Diagnostic Interview		x								
SITBI – Suicidality Interview		x	x	x	x	x	x	x	x	x
Randomization			x							
Administer Study Agent E2 (or placebo) Patch				x	x		x	x		
Dispense Study Agent P4 (or placebo) Pills					x	x		x	x	
Height/Weight		x								
E2/P4 Serum Measure				x	x	x	x	x	x	x
CESD - Depression Self-Report				x	x	x	x	x	x	x
BHI – Hopelessness Self-Report				x	x	x	x	x	x	x
STAI – Anxiety/Threat Sensitivity Self-Report				x	x	x	x	x	x	x
SSES – Negative Social Appraisals Self-Report				x	x	x	x	x	x	x
UPPS-P – Impulsivity/Inhibitory Control Self-Report				x	x	x	x	x	x	x
FT-IRAP – Hopelessness Task				x	x	x	x	x	x	x
SAR-IAT – Negative Social Appraisal Task				x	x	x	x	x	x	x
SST – Inhibitory Control Task				x	x	x	x	x	x	x
DPT – Threat Sensitivity Task				x	x	x	x	x	x	x
Adverse Event/Side Effect Evaluation				x	x	x	x	x	x	x

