**Study Design (see figure at right; top = naturally occurring cyclicity of E2/P4 under placebo, bottom = E2/P4 withdrawal prevention using exogenous E2/P4). THIS IS NOT A CLINICAL EFFICACY TRIAL.** However, a within-person crossover RCT design with transdermal 17 $\beta$ -E2 and oral micronized P4 (or placebo) will investigate the pathophysiologic role of perimenstrual steroid withdrawal in suicidal desire and action capacity. Consenting participants will be trained in the protocol, including urine ovulation testing (LH surge preceding ovulation 24-36 hours), the daily phone assessment, and the patch/pill schedule. Using a double-blind, **within-subject cross-over design**, participants will be randomized as to the order in which they receive (1) active 17 $\beta$ -E2 + P4 or (2) placebo patch/pills. The UNC Investigational Drug Services will manage the randomization and dispensing of medications. During the E2/P4 stabilization condition, for two weeks, participants will wear a weekly patch (Climara®) delivering 0.10 mg E2/24 hrs—a dose tolerated by > 94% of the 200+ women in [name] recent study (NIMHR01087619)—

and will take oral progesterone (Prometrium®) at a dose of 200 mg (100mg each morning, 100mg each evening). A higher dose (300mg/day) was well tolerated by 100% of premenopausal women in [name] prior research (NIMHR01051246). These doses will achieve (stabilize) luteal E2/P4 levels.

**Timing of Hormone Administration.** Based on home urine ovulation testing, participants will apply the first seven-day transdermal E2 patch (or placebo patch) and begin daily oral P4 (or oral placebo) seven days after urine-confirmed ovulation (cycle 1, +7) to coincide with a time in the natural cycle when E2/P4 are elevated. The goal of the active E2+P4 manipulation is to **extend and maintain the mid-luteal phase hormone profile** beyond the point in the cycle that would normally be associated with natural E2/P4 withdrawal. In the active E2/P4 condition, the luteal phase hormone profile will be maintained for 14 days by applying a new patch on day 8 (extended luteal phase spanning +7 to +21 in lower panel), preventing natural withdrawal and stabilizing E2/P4 in physiologic luteal range. The placebo condition uses the same patch/pill schedule.

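### The schedule of events (7.3.7) and the visit timeline (7.3.3) disagree on when pills are dispensed: visits 2, 3, 5 and 6 in one, visits 1 and 4 in the other

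*Combined protocol and SAP*

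**What the plan says.** **Schedule of events, Section 7.3.7.** The row "Administer Study Agent E2 (or placebo) Patch" is marked at visits 1, 2, 4 and 5. The row "Dispense Study Agent P4 (or placebo) Pills" is marked at visits 2, 3, 5 and 6.

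**Timeline, Section 7.3.3.**
- Condition 1 starts with "Study Followup Visit 1 (Day +7): Assessments, administration of study agent patch A and dispensation of pills".
- Visit 2 is "Study Followup Visit 2 (Day +14): Assessments, replacement of study agent patch A with patch B", with no pill dispensing listed.
- Then comes "Removal of study patch and end of pills on day +21", followed by "Study Followup Visit 3 (Day +22): Assessments, Pregnancy Test".
- Condition 2 has the same structure: "Study Followup Visit 4 (Day +7): Assessments, administration of study agent patch A and dispensation of pills", and no dispensing listed at visits 5 or 6.

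**Elsewhere.**
- Section 4.1 has participants apply the first patch and "begin daily oral P4 (or oral placebo) seven days after urine-confirmed ovulation".
- Sections 2.2 and 6.1.9 give a 14-day course.
- Section 6.1.10 sets up pill reminders at the first lab visit.
- Section 6.2 has research staff distribute agent according to the study schedule that follows it. Section 7.3, which carries that title, contains both the timeline and the table.

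**The concern.** None of the four pill marks in the table matches a dispensing visit in the timeline, and both dispensing visits in the timeline are blank in the table. The instruction for handing out study agent points to a section that gives two answers.

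At stake is what the active condition consists of. The trial compares natural withdrawal with combined E2/P4 stabilization. Section 10.2 states the hypothesis as the change from Lab 1 to Lab 2 within each condition, and Section 4.1 names Lab 2 under placebo against Lab 2 under active agent as the primary window for tasks and interviews. Lab 2 is visit 2 of a condition, nominally day +14. If pills were first handed out at that visit, the interval between the two labs would contain the patch but no oral agent.

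**Working it through.** **Inputs.** Visit days +7, +14 and +22, with windows of ±2 days (7.1.1, 7.3.3). End of pills on day +21 (7.3.3). Planned course of 14 days (2.2, 6.1.9). Two pill doses per day (4.1).

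**Step 1: column positions in 7.3.7.** The header has 11 cells: the procedure label, screening, enrollment, randomization, six visits and the final visit. The patch and pill rows also have 11 cells each.

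| Row | Visits marked |
|---|---|
| Patch, 7.3.7 | 1, 2, 4, 5 |
| Pills, 7.3.7 | 2, 3, 5, 6 |
| Pills, 7.3.3 timeline | 1, 4 |

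The pill row has the patch row's pattern moved one column to the right.

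**Step 2: the plan's own figure.** Course length is the end of pills minus the first dispensing day. With the timeline, 21 − 7 = 14 days, which reproduces the stated duration.

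**Step 3: the table's version, at nominal days.** First dispensing at visit 2 or 5 gives 21 − 14 = 7 days. The uncovered part is 14 − 7 = 7 of 14 days (50%). In doses, that is 7 × 2 = 14 of 14 × 2 = 28 per condition.

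**Step 4: the later marks.** Visits 3 and 6 are on day +22, and 22 − 21 = 1 day after pills end.

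**Step 5: visit windows.**
- The shortest visit 1 to visit 2 gap is (14 − 2) − (7 + 2) = 3 days.
- The longest is (14 + 2) − (7 − 2) = 11 days.
- Visit 3 can fall on days +20 to +24, that is, from 1 day before to 3 days after day +21.

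**Step 6: which analyses are touched.** The Lab 2 − Lab 1 contrast (10.2) spans the interval without oral agent. The daily-call endpoints (4.2.1, 10.4.2) use the final seven days of administration. At nominal days that window starts at 21 − 7 = day +14, when pills would be in hand under the table, but after a week without them.

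**Step 7: the rest of the table against the text.**
- Serum, the four tasks and the five self-reports are marked at debriefing. Section 7.1.1 lists only the SITBI there, and 7.2.1 places blood samples at the six lab visits.
- The five self-reports are blank at enrollment, where 7.1.1 lists all five.
- The SITBI is marked under randomization, where the text describes no interview.
- Height/weight is marked at enrollment only, while 7.3.3 lists weight at follow-up.

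**The case against.** The strongest reply is that the row may not be printed this way. A pattern moved by exactly one column is what a cell slip in typesetting or PDF extraction produces. The full cell count does not exclude it, because a row can gain a leading blank and lose a trailing one. The alignment of other rows gives only limited reassurance: the patch and randomization rows agree with the text, but several assessment rows do not (step 7). This stands. It is why the published table must be looked at first. The other mismatches also fit a table that was never proofread against the text, so they do not settle the matter either way.

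Second, Sections 2.2, 4.1, 6.1.9, 6.1.10 and 7.3.3 all tell one story, and nothing says that 7.3.7 overrides 7.3.3. At a single site that sets up pill reminders at the first lab visit and asks about compliance on daily calls, the mismatch would probably surface early. This also stands: the harm is conditional. It does not remove the contradiction, since 6.2 directs staff to a section holding both versions.

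A reader might infer more than the documents support:
- *That participants will miss half of their pills.* The 50% holds only at nominal days and only if the table is followed.
- *That progesterone would start after part of the natural fall.* The text gives no day for that fall.
- *That pills handed out on day +22 would spoil a follow-up designed to observe withdrawal.* Section 4.1 says when the calls end, not that this is their purpose, and use of such pills is only a possibility.
- *That the daily-call primary endpoints would be measured without oral agent.* Step 6 shows otherwise at nominal days.

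**Conclusion.** The concern holds as an internal contradiction in an operative table, not as a criticism of the design. As extracted, 7.3.7 and 7.3.3 agree on no pill-dispensing visit. If the table were followed at nominal visit days, 7 of 14 days in each condition would have no oral agent, with a visit 1 to visit 2 gap of 3 to 11 days within the windows. The Lab 1 to Lab 2 contrast would not test combined E2/P4 stabilization, and two of the four dispensing marks would fall one day after the stated end of pills. This could affect every participant in both periods.

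The conclusion rests on two assumptions: that the printed table matches the extracted one, and that staff work from the table rather than the timeline. Estimand, analysis method and sample size are not affected by the discrepancy as such. It still needs correcting, because it concerns the days on which study agent reaches participants.

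**What to change.** 1. Check the pill row in the published table by eye, to rule out an extraction slip.
2. If the row is printed as extracted, reconcile it with 4.1 and 7.3.3 so that table and timeline give the same dispensing visits and the same end of pills. The sponsor decides which text governs; no schedule is proposed here.
3. In the same pass, reconcile the other marks that disagree with 7.1 to 7.3: serum, tasks and self-reports at debriefing, self-reports missing at enrollment, SITBI under randomization, and weight at follow-up.
4. Issue the reconciled table to study staff and the investigational pharmacy.

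The cost is a one-row correction plus a proofread of the table, issued as an amendment. The pill-row correction adds no procedures and no participants.
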